3.2. Study endpoints

The study objectives and corresponding endpoints are shown in the [Table 2-1](#).

3.3. Study interventions

The highest approved dose regimen of SC dupilumab has been selected for this study (300 mg Q2W).

Participants will receive;

- Dupilumab 600 mg (2 x 300 mg dupilumab subcutaneous injections) on Day 1 (ie, the loading dose), followed by 1 dupilumab injection of 300 mg every two weeks (Q2W) until Week 24.
- Matching placebo for dupilumab (2 x 2 mL placebo subcutaneous injections) on Day 1 (loading dose), then 1 placebo injection Q2W until Week 24.

A home dosing diary will be provided to collect information related to at home injections.

Non-investigational medical products (NIMP)

Participants should be treated with medium to high dose of inhaled corticosteroids (ICS) in combination with a second controller (ie, Long-Acting Beta-Agonists (LABA), Leukotriene Receptor Antagonists (LTRA), theophylline). A third controller is allowed but not mandatory. The dose regimen should be stable for ≥1 month before V1, during the screening and treatment period. Short-acting β2 agonists may be used as rescue medication during the study if needed.

In case of severe asthma exacerbations, the systemic corticosteroids are allowed as rescue medication as well. An asthma background therapy diary will be provided to collect information related to NIMP use.

3.4. Dose adjustment/modifications

Not applicable.

[figure not shown]
4. GENERAL STATISTICAL CONSIDERATIONS

4.1. Sample size

In order to preserve the type I error at 0.05 level for the two primary endpoints, a hierarchical testing procedure will be applied at a 2-sided 5% significance level. The hierarchy of the tests for primary endpoints will be:

1. Proportion of participants achieving response of FeNO <25 ppb at Week 24
2. Percentage change from baseline to Week 24 in untrimmed distal [s]iVaw at TLC

After the significance has been achieved for 2 primary endpoints, the other selected secondary endpoints will be tested following a hierarchical testing procedure at a 2-sided 5% significance level. The whole list of secondary endpoints to be tested in the hierarchical order will be specified in [Section 8.2.5](#).

4.2. Randomization, stratification, and blinding

Randomization will be stratified by ICS dose level (medium/high- no less than 40% in 'high ICS' stratum) and region (EE/ROW - no more than 40% participants in EE stratum).

A randomized participant is defined as a participant who is registered and assigned with a study intervention kit number from the centralized treatment allocation system regardless of whether the intervention kit was used, as documented from its log file. A participant cannot be randomized more than once in the study.

4.3. Analysis set

Participants exposed to Investigational Medicinal Product (IMP) before or without being randomized will not be considered randomized, will not be included in any analysis set and will be reported in listings under a study intervention group named "not randomized but treated". However, if these participants experienced any safety event, they would be documented separately in the Clinical Study Report (CSR).

Participants randomized but not treated will be included in all efficacy analyses. These participants will be analyzed for efficacy analyses according to the study intervention group to

which they are allocated by the Interactive Voice Response System/Interactive Web Response System (IVRS/IWRS).

4.3.1. Screened analysis set

The Screened analysis set includes all participants who sign the Informed Consent Form (ICF).

4.3.2. Intent-to-Treat (ITT) analysis set

The Intent-to-Treat (ITT) analysis set consists of randomized participant (participant with a study intervention kit number allocated and recorded in the IVRS/IWRS database, regardless of whether the study intervention kit was used or not). Participants in the ITT analysis set will be analyzed according to the study intervention group allocated by randomization. This analysis population will be applied to all efficacy analyses.

4.3.3. Safety set

The Safety set includes all randomized participants who received at least 1 injection of IMP. Participants will be analyzed according to the study intervention they actually received. Randomized participants for whom it is unclear whether the study medication was taken will be included in the safety set as randomized. For participants receiving more than one IMP during the study (ie, placebo and dupilumab), the actual study intervention group for as treated analysis will be the dupilumab group.

4.4. Reporting conventions

Statistical analysis will be performed using SAS® Version 9.4 or higher.

Standardized and validated SAS macros will be used to set-up table, listing, figure (TLF) formats (headers/footers and tabulation format) and tabulate the summaries. All tables and listings will be independently validated using double programming; all figures will be independently validated manually.

4.4.1. Study intervention labels

The following study intervention labels will be used in the Tables, Figures and Listings:

Table 4-1 Study intervention labels

Study intervention order	Study intervention group	Study intervention label
1	Placebo	Placebo
2	Dupilumab 300 mg q2w	Dupilumab 300 mg q2w
3	Total	Total

4.4.2. Visit naming conventions

The electronic Case Report Form (eCRF) visit label will be used to classify the assessments.

4.4.3. Visit windows

The visit windows as defined in [Section 15.5](#) will be applied to all endpoints.

4.4.4. Unscheduled visits

Unscheduled visit measurements will be used in the analysis on efficacy variables and will be included in the by-visit summaries for the safety variables if they are re-allocated to scheduled visits according to the visit window definitions in [Section 15.5](#).

4.4.5. Display of data summary and analysis

Continuous variables will be summarized using descriptive statistics, including the following: sample size (n), mean, standard deviation (SD), median, first quartile (Q1), third quartile (Q3), minimum and maximum for each study intervention group.

All mean, Q1, Q3 and median values will be formatted to one more decimal place than the measured value. SD values will be formatted to two more decimal places than the measured value. Minimum and maximum will be formatted to the same number of decimal places as the measured value.

95% confidence intervals (CI) will be two-sided and displayed to the same level of precision as the statistic they relate to. If an estimate or a CI is not estimable, it will be presented as 'NE'. If neither an estimate, nor its CI are estimable, it will be presented as simply 'NE', not displaying 'NE' twice.

The p-values will be two-sided and will be rounded to three decimal places. If a p-value is less than 0.001 it will be reported as '<0.001'. If a p-value is greater than 0.999 it will be reported as '>0.999'.

Categorical and ordinal data will be summarized using the counts and percentages. When count data are presented, the percent will be suppressed when the count is zero in order to draw attention to the non-zero counts. A row denoted 'Missing' will be included in count tabulations for demographics, baseline characteristics and compliance to account for missing values.

No percentages will be displayed on the 'Missing' rows and the percentages on the other rows will be based on the number of non-missing observations. Unless otherwise specified, the denominator for all other percentages will be the number of participants in that study intervention within the specific analysis set of interest. All percentages will be rounded to one decimal place. The number and percentage of responses will be presented in the form xx (xx.x), where the percentage is in the parentheses. When the numerator is equal to the denominator, the percentage should be presented as (100) instead of (100.0), unless otherwise specified.

All listings will be sorted for presentation in order of assigned study intervention arm, study center number, participant number and date of procedure or event.

4.4.6. Baseline, study day and duration derivations

For efficacy parameters, the baseline value is defined as the last available valid (non-missing) value up to and including the date of first dose of IMP. For participants randomized but not treated, the baseline value is defined as the last available value up to and including the day of randomization.

For safety parameters, the baseline value is defined as the last available valid (non-missing) value up to and including the date of first dose of IMP.

If multiple valid values of a variable (efficacy or safety) exist within a same day (and the recorded times of measurement do not enable to identify which of them is the last assessment), the value measured during the scheduled visit will be used as Baseline in the analysis. If none of those values were assessed during a scheduled visit, then all these measurements will be used for the analysis and the average will be calculated to derive the baseline value.

Baseline safety and baseline efficacy results are presented in the safety and efficacy analyses.

The reference day (denoted as Day 1) for the calculation of extent of exposure and study day for AE listings will be the day of the first administration of IMP:

- Extent of exposure (see [Section 7.2.1](#))
- Study day for AE listing: AE onset date – first administration date of IMP +1

The reference day (denoted as Day 1) for the calculation of study day of efficacy assessments will also be the day of the first administration of IMP (except for participants randomized but not exposed).

- For visit prior to the first administration of IMP, study day = assessment date – the first administration of IMP.
- For visit at or after the first administration of IMP, study day = assessment date – the first administration of IMP +1.

Note: For participants randomized but not treated, the reference day will be the randomization date.

Intervals that are listed and/or tabulated in weeks will be transformed from days to weeks by using (without rounding) the following conversion formula:

$$\text{WEEKS} = \text{DAYS} / 7$$

Intervals that are listed and/or tabulated in months will be transformed from days to months by using (without rounding) the following conversion formula:

$$\text{MONTHS} = \text{DAYS} / 30.4375$$

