In specific situations, between the protocol-scheduled on-site visits, interim visits may be required for IMP dispensing. As an alternative to the on-site IMP dispensing, IMP may be supplied from the site to the participant via a Sponsor-approved courier company where allowed by local regulations and approved by the participant.

For a regional or national emergency declared by a governmental agency that results in travel restrictions, confinement, or restricted site access, contingency measures are included in Appendix 9 ([Section 10.9](#)).

Investigational medicinal product will be administered by the Investigator/health care professional or designee following clinical procedures and blood collection. Participants should be monitored for at least 30 minutes after administration of all IMP injections at site. The monitoring period may be extended as per country-specific or local site-specific requirements.

Subcutaneous injection sites should alternate between the upper thighs, 4 quadrants of the abdomen or the upper arms, so that the same site is not injected twice during consecutive administrations. Injection in the upper arms can only be done by a trained person (caregiver) or health care professional but not by the participants themselves.

The Investigator or delegate will train the participant (or caregiver) how to prepare and inject IMP at Visit 2 and retrain if needed during the treatment period. The site staff will inject the first dose of the 2 injections at D1. The participant (or caregiver) will perform the second injection under the supervision of the Investigator or delegate. This training must be documented in the participant's study file. Participant or caregiver should be trained by the site staff to recognize potential signs and symptoms of hypersensitivity reaction and to self-monitor/monitor at home for at least 30 minutes (or longer per country specific or local site-specific requirements) following injection. In case of hypersensitivity symptoms, the participant should contact healthcare provider/emergency.

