9.3. Vital sign measurements

Vital signs including weight, heart rate (HR), sitting systolic (SBP) and diastolic blood pressure (DBP), temperature and respiratory rate, will be collected at screening visit, at baseline visit (Day 1) before receiving the IMP and then at all subsequent visits.

The vital sign results will be summarized using descriptive statistics for each visit or study assessment (baseline, each-post-baseline time point).

The Potentially Clinically Significant Abnormalities (PCSA) at any time during the TEAE period will be summarized using number and percentage. The PCSA are provided in [Section 15.7](#).

All measurements collected during the TEAE period, including values from unscheduled visits, will be considered for the PCSA summaries. The summaries will include participants who have at least 1 assessment performed during the TEAE period. When a PCSA definition involves a change from baseline value, participants must also have a baseline value to be included in the summaries.

A listing of participants with at least 1 post-baseline PCSA will be provided and will display the participant's full profile (all participant's results) over time of all vital sign parameters.

Individual data listings will include the following flags:

- Baseline values will be flagged “B”,
- Parameter values reaching a PCSA limit will be flagged (+, or - depending of the direction).

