15.4.8. Handling of potentially clinically significant abnormalities

For PCSAs with 2 conditions, one based on a change from baseline value or a normal range and the other on a threshold value, with the first condition being missing, the PCSA will be based only on the second condition.

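### The SAP safety baseline is cut off by date rather than time of first dose, so an unscheduled post-injection vital sign can become baseline; and SAP 9.3 and 15.4.8 conflict when a baseline is missing

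*SAP*

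**What the plan says.** **Baseline.** For safety parameters SAP 4.4.6 uses "the last available valid (non-missing) value up to and including the date of first dose of IMP". No text there requires the value to precede the injection. A same-day tie-break exists, but it applies only if "the recorded times of measurement do not enable to identify which of them is the last assessment"; in that case "the value measured during the scheduled visit will be used as Baseline in the analysis".

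**Timing of readings.** SAP 9.3 places vital signs at screening, "at baseline visit (Day 1) before receiving the IMP and then at all subsequent visits". Protocol 8.2.2 likewise puts blood pressure and pulse ahead of dosing at clinic visits. No post-dose vital sign appears in either schedule of procedures. Protocol 6.1 adds observation only: "Participants should be monitored for at least 30 minutes after administration of all IMP injections at site".

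**PCSA summaries.** The treatment-emergent period in SAP section 9 opens at the first administration. SAP 9.3 then states: "All measurements collected during the TEAE period, including values from unscheduled visits, will be considered for the PCSA summaries". In SAP 15.7 each HR, SBP and DBP criterion combines a threshold with a minimum change from baseline.

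**Missing baseline.** Where a criterion involves change, SAP 9.3 says "participants must also have a baseline value to be included in the summaries". SAP 15.4.8, on criteria with two conditions, says that "with the first condition being missing, the PCSA will be based only on the second condition".

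**The concern.** If a participant feels unwell after the loading dose and a reading is taken and entered with its time, that reading is the latest on the first-dose date. By the wording of SAP 4.4.6 it is the baseline. By SAP 9.3 it is also an on-treatment measurement eligible for the PCSA table. Compared with itself, it shows no change.

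The situation is foreseeable. Participants are watched on site after the injection, and systemic hypersensitivity is an important identified risk in protocol 2.3 and an adverse event of special interest (AESI) in protocol 8.3. Other outputs do not restore the reading: the first vital-sign analysis window in SAP 15.5 opens at study day 2, and the full-profile listing in SAP 9.3 covers only participants who already have a post-baseline PCSA.

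The missing-baseline question is separate. Two programmers following different sections could produce different numerators and denominators for the same PCSA table.

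**Working it through.** The plan states no figure here, so there is nothing to reproduce. The check applies the SAP 15.7 criteria under two baselines: (a) SAP 4.4.6 as written and (b) the last value before the first injection. The readings are illustrative assumptions, not document figures.

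Criteria used:
- low SBP: value ≤95 mmHg and decrease ≥20
- high SBP: value ≥160 mmHg and increase ≥20
- high HR: value ≥120 bpm and increase ≥20

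**Step 1. The reading that serves as baseline.** Change = v − v = 0. The SBP and HR criteria need a change of at least 20 and the DBP criteria at least 10. Running every value from 20 to 259 through the HR, SBP and DBP rules gives no flag.

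**Step 2. Cases.**

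| Case | (a) SAP 4.4.6 as written | (b) Pre-dose baseline |
|---|---|---|
| SBP 125 pre-dose, one timed post-dose 90 | 90 − 90 = 0, no flag | 90 − 125 = −35, flag |
| HR 80 pre-dose, one timed post-dose 125 | 125 − 125 = 0, no flag | 125 − 80 = +45, flag |
| SBP 125 pre-dose, post-dose 90 then 122 | 90 − 122 = −32, flag | −35, flag |
| SBP 125 pre-dose, post-dose 90 then 105 | 90 − 105 = −15, no flag | −35, flag |
| SBP 125 pre-dose, post-dose 90, times unusable, scheduled value used | −35, flag | −35, flag |
| Later visit SBP 92 (pre-dose 125, Day 1 post-dose 90) | 92 − 90 = +2, no flag | 92 − 125 = −33, flag |
| Later visit SBP 160 (pre-dose 145, Day 1 post-dose 90) | 160 − 90 = +70, flag | 160 − 145 = +15, no flag |
| Scheduled pre-dose readings only | same baseline | same baseline |

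The rule can therefore miss an abnormality on Day 1, miss one later, or create one later. It does nothing when only scheduled readings exist.

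**Step 3. Dosing on the day after Visit 2.** Both schedules let the loading dose move to D1+1 when the scan slips. If vital signs were taken only the day before (an assumption), a single post-dose reading is the only value on the first-dose date. It becomes baseline even without a recorded time, because the tie-break needs several values on one day.

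**Step 4. Missing baseline.** If an HR, SBP or DBP value is observed but its change is missing, the baseline must be missing. SAP 9.3 and 15.4.8 therefore address the same participants. Take SBP 165 with no baseline: SAP 9.3 leaves the participant out of the table; SAP 15.4.8 counts a PCSA because 165 ≥ 160. SAP 15.7 is the SAP's only PCSA table, and HR, SBP and DBP are its only two-condition parameters, so 15.4.8 has no other criteria to govern.

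**Step 5. Scale of one participant.** With about 97 randomised 2:1, the arms are about 97 × 2/3 ≈ 65 and 97 × 1/3 ≈ 32. One reclassified participant moves a percentage by 1/65 = 1.5 points on dupilumab or 1/32 = 3.1 points on placebo. This is the resolution of the table, not an estimate of how many are affected.

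**The case against.** The strongest reply is that no planned measurement triggers the baseline defect. Scheduled Day 1 readings precede the dose in both documents, and the monitoring requirement in protocol 6.1 names no vital sign to be measured or recorded. This stands and limits the point to unscheduled readings.

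A reader might infer that any Day 1 post-injection change is impossible to flag. The documents do not support that. Only the last value of the day becomes baseline, so an earlier low reading followed by recovery can still be flagged. When times cannot identify the last of several values, SAP 4.4.6 already uses the scheduled value.

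A reader might also infer that an acute reaction would be hidden. That goes too far as well. Hypersensitivity and anaphylaxis are AESIs, reported by the investigator within 24 hours and found by the searches in SAP 15.6. Events with incomplete onset default to treatment-emergent. None of this depends on the vital-sign baseline.

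On missing baselines, screening vital signs also qualify under SAP 4.4.6, so both visits would have to lack the parameter. That stands: the case is rare. It can further be argued that SAP 15.4.8 sets flags for listings while 9.3 sets the table population. That would be workable, but the SAP does not say it, and 15.4.8 is not limited to listings.

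**Conclusion.** The point holds in a narrow form. SAP 4.4.6 has no pre-dose limit. A post-injection vital sign that is the last value on the first-dose date by recorded time, or the only one on that date, becomes baseline. That reading cannot be flagged, and later PCSA classifications can be wrong in either direction. Separately, SAP 9.3 and 15.4.8 give opposite results in the PCSA summary for a participant without a baseline, with no stated precedence.

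The baseline finding assumes that such an unscheduled reading is taken and entered in the database. The documents give no basis for how often that happens, and the number may be zero. The missing-baseline conflict is certain on the text but will rarely be exercised. The effect is confined to the vital-sign safety tables; no efficacy inference, sample size or type I error is affected.

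**What to change.** 1. In SAP 4.4.6, define the safety baseline as the last valid value before the date and time of the first IMP injection. Where time is missing, use the value scheduled before dosing, including when the loading dose moves to D1+1. This fits the rest of the plan: protocol 9.4.2 starts the treatment-emergent period at the date and time of first dose, and SAP 15.4.5 expects that time to be collected.

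2. Keep one missing-baseline rule for criteria that involve change. Either retain SAP 9.3 and withdraw 15.4.8 for those criteria, or the reverse. State the resulting PCSA denominator. If 15.4.8 is meant for listings only, say so.

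The cost is about two sentences and one derivation, made before database lock. Baselines do not change where only pre-dose readings exist.

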4.4.7. Change from baseline and percent change from baseline

Change from baseline is defined as:

$$\text{Change from baseline} = \text{Value at specific time point} - \text{Baseline value}$$

Percent change from baseline is defined as:

$$\text{Percent change from baseline}(\%) = \frac{\text{Value at specific timepoint} - \text{Baseline value}}{\text{Baseline value}} \times 100\%$$

4.5. Intercurrent event types

Table 4-2 specifies the types of Intercurrent events (IcEvs), and associated labels, used to define the estimands.

Table 4-2 Intercurrent event types

Label	Intercurrent Event Type
IcEv1 (discontinuation of study intervention due to Covid-19)	Premature study intervention discontinuation due to Covid-19 pandemic before Week 24
IcEv2 (discontinuation of study intervention not due to Covid-19)	Premature study intervention discontinuation not due to Covid-19 pandemic before Week 24

5. PARTICIPANT DISPOSITION

5.1. Disposition

The participant disposition will be summarized for the ITT analysis set by study intervention group and overall using number and percentage. This section describes participant disposition for both participant study status and the participant analysis sets.

For participant study status, the number and percentage of participants in the following categories will be presented:

- Screened participants
- Screen failure participants
- Participants treated without being randomized
- Randomized participants
- Randomized but not treated participants
- Randomized and treated participants
- Participants who have completed the study intervention period
- Participants who discontinued the study intervention period and the main reason for study intervention discontinuation. Relationship with COVID-19 will be reported for “Adverse Event” and “Other” reasons.
- Participants who completed the study
- Participants who discontinued the study and the main reason for study discontinuation. Relationship with COVID-19 will be reported for “Other” reasons
- Participants who discontinued the study before Week 24
- Participants who discontinued the study after Week 24 (ie, during post-study intervention follow-up period)
- Participants who had rescue medications during the study intervention period:
 - Participants who have completed the study intervention period and had rescue medications
 - Participants who did not complete the study intervention period and had rescue medications
- Final Study Status

For screened, screen failure, and participants treated without being randomized, percentages will be calculated using the number of screened participants as the denominator for overall only.

All other categories of participants will be presented by randomized study intervention group and for overall whilst the percentages will be calculated using the number of randomized participants, within each study intervention group and overall, as denominator. Reasons for study intervention and study discontinuation will be supplied in the disposition table showing number and percentage by study intervention group.

A summary of all the analysis sets for safety and efficacy (ITT) will be summarized for the ITT analysis set by study intervention group and overall using number and percentage.

Participants with permanent study intervention and study discontinuation (early withdrawals) will be identified and described in separate listings (with the reason of discontinuation and the specification in case of other reason).

Additionally, trial impact (disruption) due to COVID-19 will be summarized for the ITT analysis set by study intervention group and overall using number and percentage. Participants for whom at least one of the following events occur during the study will be presented:

- Permanent end of study intervention due to COVID-19 pandemic
- Premature end of study due to COVID-19 pandemic
- Permanent end of study intervention due to AE related to COVID-19 infection
- Critical or major protocol deviation due to COVID-19 pandemic

Some safety (adverse events) analyses will also be repeated on the subgroup of safety participants according to trial impact (disruption) due to COVID-19 pandemic (see [Section 9.1](#)).

The disposition of screened participants by country and site will be summarized for the screened analysis set using number and percentage.

A summary table to show participant disposition by visit according to trial impact (disruption) due to COVID-19 pandemic (visit not done, visit partially done on site, visit partially done by phone and visit done but delayed) will be provided overall and by country for the ITT analysis set.

